8.3.4 Time Period and Frequency for Event Assessment and Follow-up

AEs will be recorded from the time the ICF is signed until the end of the follow-up period. AEs will be assessed at each study visit, and subjects should be encouraged to contact the study site to report AEs that occur between scheduled visits. AEs that occur in the time period between informed consent and the first dose of study drug should be recorded but will not be considered TEAEs. If the AE occurs on the date of the first dose of study drug, the time of onset (before or after intake of study drug) will be captured.

After the initial AE/SAE report, the Investigator is required to proactively follow each subject at subsequent visits/contacts. All AEs/SAEs will be followed until resolution, stabilization, the event has been shown to be unrelated to study treatment, or the subject is lost to follow-up (as defined in [Section 7.3](#)).

8.3.5 Adverse Event Reporting

The Investigator is to report all AEs, whether volunteered by the subject, discovered through questioning, or directly detected, that occur in the time period specified in [Section 8.3.4](#) and according to classifications described in [Section 8.3.3](#).

Non-serious AEs that don't require immediate reporting are to be reported on the AE eCRF.

SAEs and AESIs will receive special consideration in decisions about continuing, modifying, or suspending dosing/enrollment. The Investigator will notify the Sponsor within 1 day of awareness for immediate review (see [Section 8.3.6](#)).

8.3.6 Serious Adverse Event Reporting

Throughout the study, the Investigator is to report all SAEs, regardless of suspected causality, to the Sponsor within 24 hours of learning of its occurrence using the SAE Report Form in the EDC system. AESIs (see [Section 8.3.8](#)) will also be reported on the SAE Report Form in the EDC system and must be clearly differentiated from SAEs. Completion guidelines are provided in the Investigator Site File. The Investigator must assess and record the relationship of each event to study drug. Any SAE experienced after the follow-up period should be reported to the Sponsor only if the Investigator suspects a causal relationship to the study drug.

Recurrent episodes, complications, or progression of the initial SAE, regardless of when they occur, must be reported as follow-up to the original episode within 24 hours of the Investigator receiving the follow-up information. Follow-up information will also be captured in the EDC system and should describe whether the event resolved or continues, if and how it was treated, and whether the subject continued or withdrew from study participation. An SAE occurring at a different time interval or otherwise considered completely unrelated to a previously reported SAE should be reported separately as a new event.

The Sponsor will ensure that all suspected unexpected serious adverse reactions (SUSARs), determined based on the Reference Safety Information in the most recent version of the IB at the time of the event, will be reported to the competent authorities of all countries where the trial is performed and to all IRBs/ECs overseeing the conduct of the study, in accordance with FDA 21 CFR 312.32 and European Directive 2001/20/EC. These reports will be unblinded upon submission where required.

8.3.7 Reporting of Pregnancy

Any subject who becomes pregnant during the study will have study drug discontinued immediately and be withdrawn from the study. All pregnancies in female subjects or in the female partners of male subjects must be reported to the Sponsor within 24 hours of the site learning of the pregnancy. Information about pregnancies will be recorded on the Pregnancy Report Form and any follow-up information will be forwarded to the Sponsor.

For any female subject who becomes pregnant while participating in this study, the Investigator will collect information about the pregnancy and follow up with the subject to determine the outcome of the pregnancy and the status of mother and child.

Male subjects will be instructed to notify the site in the event that any female partner becomes pregnant. If any female partner of a male subject who received at least 1 dose of study drug becomes pregnant within 90 days of the male subject's last dose of study drug, the Investigator will attempt to collect information about the pregnancy. The Investigator must obtain informed consent from the pregnant partner before collecting such information. The Investigator will also

attempt to follow up with the female partner to determine the outcome of the pregnancy and the status of mother and child.

Generally, follow-up will not be required for longer than 6 to 8 weeks beyond the estimated delivery date. Any termination of the pregnancy will be reported regardless of fetal status (presence or absence of anomalies) or indication for the procedure.

Pregnancy in itself is not regarded as an AE. However, a pregnancy complication is an AE, and congenital abnormalities/birth defects or spontaneous miscarriages should be reported as SAEs. Elective termination of a pregnancy is not considered an AE. While the Investigator is not obligated to actively seek this information in former study subjects, he or she may learn of such an SAE through spontaneous reporting.

8.3.8 Adverse Events of Special Interest

AESIs must be monitored on an ongoing basis. These events will be reported with narratives, allowing for the collection of additional information, as warranted. The following may be considered AESIs for this study:

- Significant liver chemistry changes that do not satisfy study drug stopping rules (see [Section 7.1.1](#) and [Section 13.2](#)). Cases of Hy's Law should be reported as SAEs.
- Suicidality as indicated by Type 3, 4, or 5 ideation on the C-SSRS (see [Section 7.1.3](#) regarding study drug stopping criteria for suicidality and [Section 8.2.6.1](#) regarding the C-SSRS). This safety finding will be reported as an AESI if it is not considered an SAE definition (e.g., resulting in hospitalization).
- Depression or anxiety that is moderate or severe (CTCAE Grade 2 or higher), as assessed by the Investigator (see [Section 7.1.4](#) regarding study drug stopping criteria for depression or anxiety). This will be reported as an AESI if it is not considered an SAE (e.g., resulting in hospitalization).
- Adverse events of adrenal insufficiency will be reported on a separate Adrenal Insufficiency Form. Additionally, symptoms of adrenal insufficiency will be reported as SAE if they necessitate parental GC administration by a health care professional and two of the following criteria are met: hypotensive (systolic blood pressure <100 mmHg); nausea or vomiting; severe fatigue; documented hyponatremia, hyperkalemia, or hypoglycemia. If hospitalization was required or the event of adrenal insufficiency is deemed to be an important medical event, life-threatening, results in a persistent or significant disability/incapacity or death, it should also be reported as an SAE.
 - For SAEs of adrenal insufficiency, records from the office of health care provider, emergency facility or hospital the following information should be obtained as source documents to provide the following information:
 - Was stress dosing employed prior to the adrenal insufficiency event? If yes, what were the GC dose and duration of dosing and the cause for stress dosing prior to seeking medical attention?
 - What type, dose and route of parental GC was administered and the duration of administration?

- What concomitant medications were administered?
- What clinical laboratory results are available?
- What AEs occurred?
- What was the duration of stay if admitted to the hospital?
- What was deemed to be the inciting factor leading to adrenal crisis?

For non-SAEs of adrenal insufficiency, all symptoms and findings on physical examination, vital sign collection and/or laboratory assessments leading to the diagnosis of adrenal insufficiency will be collected.

Adverse events or other conditions that lead to GC stress dosing should not be reported as AEs of adrenal insufficiency since the stress dosing is done to prevent, not treat, adrenal insufficiency. If an AE, such as an infection, results in GC stress dosing, the AE should be captured in the Adverse Event CRF. The following additional information will be collected in a patient diary during episodes of GC stress dosing: start and stop date, concomitant medications, cause for stress dosing (e.g., infection, strenuous exercise, emotional stress, pain, surgery) and concurrent AEs. Adverse events resulting in stress dosing will be reported on the Adverse Event CRF.

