4.1.4.4 Stress Dosing of Glucocorticoid

During times of clinically significant physical stress such as intercurrent illness with fever, surgical procedures, or significant trauma, subjects may take extra GC (in the form of HC) consistent with the “sick day guidelines” for prevention of adrenal crisis shown in [Table 2](#) ([Bornstein 2016](#)). Sites may employ variations on these guidelines, consulting with the Medical Monitor, if possible, in non-urgent situations. The Sponsor will provide all subjects with oral HC for the purposes of stress dosing ([Section 6.2.2](#)). For subjects who are not taking HC as their background GC regimen, the stress dose of HC should be estimated based on the relative potencies of GCs specified in [Table 1](#).

The stress doses recommended in [Table 2](#) are meant to *replace* a subject’s usual daily GC dose; they are NOT taken *in addition* to the subject’s usual daily GC dose. When taking the stress dose orally, the subject should take the entire stress dose using HC tablets from the bottle provided by the Sponsor. Daily replacement dosing from the subject’s or Sponsor-provided GCs should be temporarily held during stress dosing and reinstated as soon as the stress dosing period ends.

While all GC stress doses should be entered into the EDC, changes to usual daily GC dose only need to be entered into EDC when there is a definitive long-term, chronic alteration in the usual daily GC dosing regimen.

Table 2. Sick Day Guidelines for Stress Dosing of Hydrocortisone

Condition	Stress Dosing of Hydrocortisone
Home management of fever >38 °C (>100.4 °F) or illness requiring bed rest, when requiring antibiotics for an infection, or before undergoing a minor outpatient procedure (eg, dental work)	
 Approximately double the routine oral GC dose (and give as HC) until recovery (usually 2 to 3 days) For fever >39 °C (102.2 °F) only, approximately triple the routine oral GC dose (and give as HC) until recovery (usually 2 to 3 days)¹ Increase consumption of electrolyte-containing fluids and simple and complex carbohydrates (El-Maouche 2018), as tolerated
Unable to tolerate oral medication due to gastroenteritis or trauma	
 HC 100 mg IM or SC
Minor to moderate surgical stress	
 HC 25 to 75 mg/24 hours (usually 1 to 2 days)

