Major surgery with general anesthesia, trauma, or disease that requires intensive care	
 HC 100 mg IV injection, followed by HC 200 mg/24 hours (via continuous IV infusion or 50 mg bolus every 6 hours IV or IM) Weight-appropriate continuous IV fluids with 5% dextrose and 0.2% or 0.45% NaCl Rapid tapering and switch to oral regimen depending on clinical state
Acute adrenal crisis	
 HC 100 mg IV injection, followed by HC 200 mg/24 hours (via continuous infusion or 50 mg every 6 hours IV or IM), reduced to HC 100 mg/day the following day Rapid infusion of 1000 mL isotonic saline within the first hour or 5% glucose in isotonic saline, followed by continuous IV isotonic saline guided by individual patient needs For hypoglycemia: 0.5 to 1 g/kg dextrose or 2 to 4 mL/kg of D25W (maximum single dose 25 g) infused slowly at rate of 2 to 3 mL/min Cardiac monitoring: rapid tapering and switch to oral regimen depending on clinical state

Abbreviations: D25W, dextrose 25% in water; GC, glucocorticoid; HC, hydrocortisone; IM, intramuscular; IV, intravenous; SC, subcutaneous.

¹ When tripling the routine oral GC dose, the HC stress dose should be rounded up to the next highest 10-mg HC tablet.

To prevent hypoglycemia, the subject should drink small amounts of clear sugar-containing liquids frequently and/or consume carbohydrates if the subject is able, glucose monitoring should be considered, and IV sodium and glucose replacement may be required ([Clayton 2002](#); [Merke and Bornstein 2005](#); [Keil 2010](#)).

Day-to-day physical or psychological stressors, such as a short-term strenuous activity or school examinations, generally do not require increased GC dosing ([Clayton 2002](#); [Crown & Lightman 2005](#); [Merke and Bornstein 2005](#)).

Subjects will maintain stress dosing until symptoms subside (or according to the clinical judgment of the treating physician), then return to their usual GC regimen. Any scheduled lab draws should be delayed until 5 to 7 days after subjects first return to their usual GC regimen. Any study visit delayed because of stress dosing will not be considered a protocol deviation. Extra unscheduled study visits for safety follow-up may be conducted in the interim.

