In the absence of any clear explanation for the subject's acute adrenal insufficiency, the Investigator should discontinue study drug. This will be considered an AESI (see [Section 8.3.8](#)).

Adverse events or other conditions that lead to GC stress dosing should not be reported as AEs of adrenal insufficiency since the stress dosing is done to prevent, not treat, adrenal insufficiency.

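### Protocol 7.1.5 and 8.3.8 bar conditions that lead to stress dosing from adrenal insufficiency reporting, yet the stress-dosing table includes acute adrenal crisis, which the same sections treat as adrenal insufficiency.

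*Protocol*

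**What the plan says.** **The exclusion.** Protocol 8.3.8 says "Adverse events or other conditions that lead to GC stress dosing should not be reported as AEs of adrenal insufficiency", with the reason "since the stress dosing is done to prevent, not treat, adrenal insufficiency". Protocol 7.1.5 carries the same rule: such events "should not be reported as AEs of adrenal insufficiency". Section 8.3.8 adds that adverse events resulting in stress dosing go on the Adverse Event CRF.

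**The stress-dosing table.** Table 2 in Protocol 4.1.4.4 is titled "Sick Day Guidelines for Stress Dosing of Hydrocortisone" and is introduced with the words "for prevention of adrenal crisis shown in". It has five rows. One is "Acute adrenal crisis", with intravenous hydrocortisone. Another is "Unable to tolerate oral medication due to gastroenteritis or trauma", with injected hydrocortisone.

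**The inclusion rules.** Protocol 7.1.5 says that when the Investigator attributes the findings to adrenal insufficiency, the event is recorded as adrenal insufficiency and its signs and symptoms go on a separate CRF. It also refers to an adrenal insufficiency AE that meets the definition of adrenal crisis, citing Table 2 for that definition. Protocol 8.3.8 sends adrenal insufficiency AEs to a separate Adrenal Insufficiency Form and says that "symptoms of adrenal insufficiency will be reported as SAE if they necessitate parental GC administration by a health care professional" and two further clinical criteria are met. It gives a second SAE route for events that need hospitalization, are life-threatening, cause disability or death, or are important medical events. Its source-document questions for adrenal insufficiency SAEs ask what precipitated the crisis.

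**The concern.** The exclusion rests on a premise, that stress dosing never treats adrenal insufficiency, and one row of the protocol's own stress-dosing table does not fit it. A site that reads the exclusion at face value would keep a treated crisis off the Adrenal Insufficiency Form. A site that follows the Investigator-judgement rule in 7.1.5 would put it on that form. Both would be following the protocol.

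This matters because the trial lowers glucocorticoid dose by algorithm (Protocol 4.1.4.3) and tests whether one arm goes lower than the other (Protocol 9.1). Protocol 7.1.5 itself foresees adrenal insufficiency from undertreatment. The classification also has consequences inside the protocol: 7.1.5 attaches study-drug, AESI and glucocorticoid-dose rules to events labelled adrenal insufficiency. The DSMB, which is asked to advise on safety trends (Protocol 10.6), would be looking at counts that depend on which sentence each site followed.

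**Working it through.** No figure in the plan bears on this point, so the check is a comparison of texts.

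**Step 1. What counts as stress dosing?** The title of Table 2 labels all five rows as stress dosing. The acute adrenal crisis row is therefore stress dosing in the protocol's own terms.

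**Step 2. Is that row preventive?** No. An acute crisis is already present when the row is used. The introduction to the table and the reason given for the exclusion both describe prevention, and neither fits this row.

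**Step 3. Apply each rule to a crisis treated under Table 2.**

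| Rule | Adrenal insufficiency? | Form |
|---|---|---|
| Exclusion sentence, 7.1.5 and 8.3.8 | Not reported as such, because the condition led to stress dosing | Adverse Event CRF (8.3.8) |
| Investigator-judgement rule, 7.1.5 | Recorded as such | Separate adrenal insufficiency CRF |
| Adrenal insufficiency and SAE text, 8.3.8 | Yes, and an SAE if either route is met | Adrenal Insufficiency Form, plus SAE report |

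The first line cannot be reconciled with the other two.

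**Step 4. Can a site resolve it from the text?** Section 7.1.5 points to Table 2 for a definition of adrenal crisis, but Table 2 lists management and contains no definition. Systolic hypotension is below 90 mmHg in 7.1.5, where it is described as associated with adrenal insufficiency, and below 100 mmHg in the SAE criteria of 8.3.8. Nothing says whether the two figures are meant to differ.

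**Step 5. Does the injection row conflict too?** Not necessarily. Injected hydrocortisone for someone who cannot keep tablets down can be preventive. That row conflicts only when adrenal insufficiency is already present, for example when an injection from a health care professional also meets the SAE criteria in 8.3.8. The direct contradiction is the crisis row, one of five.

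**Step 6. Does the SAP settle it?** No. SAP 8.3.20.4 defines a stress event as any stress dose in the diary or the concomitant medication eCRF. SAP 11.2 summarises stress dosing without separating prevention from treatment. SAP 13.1.2 tabulates AESIs by system organ class and preferred term, but liver is the only AESI type with its own named summary. The tables can show adrenal insufficiency only where a site recorded it under that label.

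**Step 7. Direction.** The exclusion can only remove events from the adrenal insufficiency category. Suppose, as an assumption, that the true risks are p1 and p0 and that a fraction f of events is classified away equally in both arms, since sites are blinded up to Week 24. The reported risk difference is then (1 − f)(p1 − p0), which is closer to zero. The documents give no value for f, p1 or p0.

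**The case against.** The strongest reply is that the intent is clear from context. The exclusion speaks of conditions that lead to stress dosing. The sentence after it in 8.3.8 uses infection as the example, and the causes listed are everyday triggers such as infection, exercise, pain and surgery. Section 8.3.8 also asks whether stress dosing was used before the adrenal insufficiency event, which separates the two. Section 7.1.5 lets the Investigator label an event as adrenal insufficiency whatever the route or setting of treatment. On this view one clarifying sentence is enough.

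Much of that stands. A careful reader can infer that only preventive sick-day dosing was meant. But the protocol does not say so: the exclusion appears twice without that limit, and the table places crisis inside stress dosing. Protocol section 5 plans about 130 sites, too many to rely on a shared inference.

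It also stands that data are not lost. The triggering event goes on the Adverse Event CRF, stress dosing is captured in the diary and the eCRF, and serious events keep an SAE route.

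A reader might go further and infer that an injection given at home escapes reporting, or that the adrenal insufficiency count turns on who gave it. The documents do not support this. The health care professional condition belongs to one SAE test only. It does not decide whether an event is adrenal insufficiency, and the second SAE route in 8.3.8 has no such condition. Nothing else in the documents contradicts that test, so there is no ground here for removing the condition.

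**Conclusion.** The contradiction is real and narrow. For a crisis treated under Table 2, the protocol both bars and requires reporting as adrenal insufficiency, and it points to two different forms. The likely result is inconsistent classification between sites, with a lean towards undercounting. That direction assumes that at least some sites apply the exclusion literally.

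The size cannot be stated. The documents give no rate of crisis or adrenal insufficiency and no basis for guessing what share would be misfiled, so any count of missed events by arm would be invention. A reader might also infer that adrenal insufficiency is the main harm expected in this trial. The documents foresee it and write rules for it, but they do not rank harms. It is enough that it is a foreseeable harm that could differ between arms if glucocorticoid doses do.

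**What to change.** Reconcile the passages as follows.

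1. In both 7.1.5 and 8.3.8, limit the exclusion sentence to preventive stress dosing given when adrenal insufficiency is not present.
2. State that an event the Investigator judges to be adrenal insufficiency, including one handled under the acute adrenal crisis row of Table 2, goes on the Adrenal Insufficiency Form even if stress dosing was used.
3. Supply the definition of adrenal crisis that 7.1.5 cites, or correct the cross-reference.
4. Reconcile the two systolic blood pressure figures, or say that they serve different purposes.
5. Correct *parental* to *parenteral* in 8.3.8.

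The cost is a protocol wording change and matching eCRF completion guidance, with probably a few more Adrenal Insufficiency Forms. No dose, stress-dosing instruction, seriousness threshold or other clinical rule needs to change to resolve the reporting conflict.

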8.4 Pharmacokinetic Assessments

A plasma sample will be collected consistently by a qualified medical professional at 8 AM (\pm 1 hour) for measurement of tildacerfont concentration at each study visit indicated in the Schedule of Treatment Period and Follow-up Activities. Samples will be collected after an overnight fast (nothing to eat after midnight) and before subjects take any morning dose of GC. Tildacerfont drug concentration will be determined by a bioanalytical laboratory using validated methods.

9 STATISTICAL CONSIDERATIONS

Statistical considerations are summarized here. A detailed description of statistical methods will be provided in the Statistical Analysis Plan (SAP).

9.1 Statistical Hypotheses

Efficacy endpoints at Week 24 will be evaluated using the following hypothesis-testing schema: The tildacerfont treatment group will be compared with the placebo treatment group. The null hypothesis is that there is no difference in the mean change from baseline to Week 24 in GC dose in HCe. The alternative hypothesis will be that there is a difference between the treatment groups.

Efficacy endpoints after 52 weeks of tildacerfont treatment will be evaluated using the following hypothesis-testing schema: The Week 52 value will be compared with the baseline value. The null hypothesis will be that there is no difference between the Week 52 and baseline values. The alternative hypothesis will be that there is a difference.

